## 2 Statistical methods

### 2.1 Data analysis general information

The final analyses will be performed by Novartis and/or a designated CRO. SAS version 9.4 or later will be used to perform all data analyses and to generate tables, figures and listings.

#### Safety evaluation part (Part 1, Japan only)

The safety and tolerability of midostaurin in combination with chemotherapy in Japan will be assessed based on the incidence of Safety Events during the safety evaluation period. A Safety Event is defined as death or serious adverse event leading to treatment discontinuation that occurs on or before Day 21 of the first consolidation cycle and that is determined by the Independent Safety Committee to be definitely or probably related to midostaurin.

All Japanese patients who signed ICF by 25Sep2018, the date when Independent Safety Committee review was held, will be assessed as patients enrolled in part 1. All patients enrolled part 1 will be listed and reviewed irrespective of the combination treatment (JALSG or RATIFY regimen). Separate SAP for Independent Safety Committee (ISC) was created.

#### Randomized part (Part 2)

In the part 2, interim, primary analyses were conducted and final analyses will be conducted.

For screening failure, patients who signed the informed consent but never started the study treatment for any reason, and non-randomized patients, the eCRF data collected will not be included in analyses, but will be reported in CSR as separate listings as appropriate.

#### Data included in the analysis

The interim analysis for efficacy were conducted when 60 patients were to be randomized (actual 62 patients) and at least 24 EFS events were documented. In case that 36 EFS events were documented before randomization completion, the interim analysis could be skipped and Novartis would plan to conduct primary analysis.

The primary analysis was performed using a pre-defined cut-off date of 30 November 2020 with the number of EFS events were documented as per amended protocol version 03 (released date 10-Sep-2020) by this date.

The end of study will occur at the latest 36 months after the start of the study treatment for the last patient. At this time, the final analysis will be performed.

All statistical analyses will be performed using all data collected in the database up to the data cutoff date. All data with an assessment date or event start date (e.g., vital sign assessment date or start date of an adverse event) prior to or on the cut-off date will be included in the analysis. Any data collected beyond the cut-off date will not be included in the analysis and will not be used for any derivations.

All events with start date before or on the cut-off date and end date after the cut-off date will be reported as 'ongoing'. The same rule will be applied to events starting before or on the cut-off date and not having documented end date. This approach applies, in particular, to adverse event

and concomitant medication reports. For these events, the end date will not be imputed and therefore will not appear in the listings.

At final analysis the cut-off date means LPLV.

### **General analysis conventions**

**Pooling of centers:** Unless specified otherwise, data from all study centers will be pooled for the analysis. Due to expected small number of patients enrolled at centers, no center effect will be assessed.

**Qualitative data** (e.g., gender, race, etc.) will be summarized by means of contingency tables by treatment group; a missing category will be included as applicable. Percentages will be calculated using the number of patients in the relevant population or subgroup as the denominator.

**Quantitative data** (e.g., age, body weight, etc.) will be summarized by appropriate descriptive statistics (i.e., mean, standard deviation, median, minimum, and maximum) by treatment group.

#### **2.1.1 General definitions**

##### **Investigational drug and study treatment**

**Investigational drug** will refer to the midostaurin. **Control drug** will refer to the placebo. The **study drug** will refer to investigational and control drugs. Whereas, **study treatment** will refer to treatment with daunorubicin, cytarabine, or midostaurin/placebo.

##### **Date of first administration of investigational drug**

The date of first administration of investigational drug is defined as the first date when a non-zero dose of investigational drug is administered and recorded on the Dosage Administration Record (DAR) eCRF. The date of first administration of study drug will also be referred as start of investigational drug.

##### **Date of last administration of investigational drug**

The date of last administration of investigational drug is defined as the last date when a nonzero dose of investigational drug is administered and recorded on DAR eCRF. The date of last administration of investigational drug will also be referred as end of investigational drug.

##### **Date of first administration of study treatment**

The date of first administration of study treatment is derived as the first date when a nonzero dose of any component of study treatment was administered as per the Dosage Administration Record (DAR) eCRF (Example: if 1st dose of midostaurin/placebo is administered on 05-Jan-2015, and 1st dose of a combination partner is administered on 03-Jan-2015, then the date of first administration of study treatment is on 03-Jan-2015). The date of first administration of study treatment will also be referred as **start of study treatment**.

## **Date of last administration of study treatment**

The date of last administration of study treatment is derived as the last date when a nonzero dose of any component of study treatment was administered as per the DAR eCRF. (Example: if the last midostaurin/placebo is administered on 15-Apr-2014, and the last dose of a combination partner is administered on 17-Apr-2014, then the date of last administration of study treatment is on 17-Apr-2014).

## **Study day**

The study day describes the day of the event or assessment date, relative to the reference start date.

The study day is defined as:

- The date of the event (visit date, onset date of an event, assessment date etc.) – reference start date + 1 if event is on or after the reference start date;
- The date of the event (visit date, onset date of an event, assessment date etc.) – reference start date if event precedes the reference start date.

The reference start date for all efficacy assessments, including PRO and performance status, is the date of randomization. The reference start date for all other assessments is the start of the study treatment.

The study day will be displayed in the data listings. If an event starts before the reference start date, the study day displayed on the listing will be negative.

## **Time unit**

A year length is defined as 365.25 days. A month length is 30.4375 days (365.25/12). If duration is reported in months, duration in days will be divided by 30.4375. If duration is reported in years, duration in days will be divided by 365.25.

## **Baseline**

For efficacy evaluations, the last non-missing assessment, including unscheduled assessments on or before the randomization date is taken as “baseline” value or “baseline” assessment. In the context of baseline definition, the efficacy evaluations also include PRO and performance status.

For safety evaluations, the last non-missing assessment, including unscheduled assessments on or before the date of start of study treatment is taken as “baseline” value or “baseline” assessment.

If patients have no value as defined above, the baseline result will be missing.

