4.1.2.2 Treatment phase

Induction therapy

All screened patients will start induction therapy with chemotherapy (daunorubicin and cytarabine) from Day 1 to Day 7, while the FLT3 mutation status is being determined.

An Interactive Response Technology (IRT) system will be used to randomize patients to the study treatment groups and the patient eligibility checklist will be embedded into the IRT randomization process.

Only randomized patients (with FLT3 mutation) will receive midostaurin/placebo, orally twice a day, on days 8 to 21.

Patients who achieve CR already with induction cycle 1 will go directly to consolidation therapy without a second cycle of induction therapy. Patients who do not achieve CR with one cycle of induction will receive a second induction cycle with same treatment than in cycle 1.

Patients not achieving CR after induction 2 will discontinue study treatment and will be followed in safety follow up and survival follow-up.

Consolidation therapy

Patients who achieved a CR after 1 or 2 cycles of induction will receive consolidation therapy with 3 cycles of high-dose cytarabine for JALSG regimen and 4 cycles of high-dose cytarabine as tolerated for RATIFY regimen.

Patients will receive midostaurin/placebo, orally twice a day, on days 8 to 21 of each cycle.

Each consolidation cycle will begin within two weeks following hematopoietic recovery (ANC $\geq 1.0 \times 10^9/L$, platelet count $\geq 100 \times 10^9/L$) but no sooner than four weeks from the beginning of the previous cycle.

For patients of age 60 years or older at the time of study entry, the dose of cytarabine may be reduced at the discretion of the investigator to $1500 \text{ mg/m}^2/\text{dose}$ for JALSG regimen and to $1000-1500 \text{ mg/m}^2/\text{dose}$ for RATIFY regimen.

Continuation therapy

After hematopoietic recovery (ANC $\geq 1.0 \times 10^9/L$, platelet count $\geq 100 \times 10^9/L$) following the final cycle of consolidation but no sooner than 14 days after the last dose of midostaurin/placebo during the last consolidation cycle, patients who maintain a CR will receive up to 12 cycles (28 days/cycle) of continuous therapy with midostaurin or placebo twice a day.

Study treatment will continue until completion of 12 cycles of continuation therapy, persistent AML, relapse, intolerable toxicity, withdrawal of consent by the patient, lost to follow up, death, or the sponsor terminates the study, whichever is earlier.

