#### **Consolidation therapy**

Patients who achieved a CR after 1 or 2 cycles of induction will receive consolidation therapy with 3 cycles of high-dose cytarabine for JALSG regimen and 4 cycles of high-dose cytarabine as tolerated for RATIFY regimen.

Patients will receive midostaurin/placebo, orally twice a day, on days 8 to 21 of each cycle.

Each consolidation cycle will begin within two weeks following hematopoietic recovery (ANC  $\geq 1.0 \times 10^9/L$ , platelet count  $\geq 100 \times 10^9/L$ ) but no sooner than four weeks from the beginning of the previous cycle.

For patients of age 60 years or older at the time of study entry, the dose of cytarabine may be reduced at the discretion of the investigator to 1500 mg/m^2/dose for JALSG regimen and to 1000-1500 mg/m^2/dose for RATIFY regimen.

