#### **Continuation therapy**

After hematopoietic recovery (ANC  $\geq 1.0 \times 10^9/L$ , platelet count  $\geq 100 \times 10^9/L$ ) following the final cycle of consolidation but no sooner than 14 days after the last dose of midostaurin/placebo during the last consolidation cycle, patients who maintain a CR will receive up to 12 cycles (28 days/cycle) of continuous therapy with midostaurin or placebo twice a day.

Study treatment will continue until completion of 12 cycles of continuation therapy, persistent AML, relapse, intolerable toxicity, withdrawal of consent by the patient, lost to follow up, death, or the sponsor terminates the study, whichever is earlier.

Safety will be assessed in this treatment phase for each patient until 30 days after the end of treatment (EOT) and will include routine safety monitoring except in case of death, loss to follow up or withdrawal of consent.

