## **Data analysis**

On analyzing laboratory, data from all sources (central and local laboratories (as applicable)) will be combined. The summaries will include all assessments available for the lab parameter collected no later than 30 days after the last study treatment administration date (see [Section 2.1.1](#)).

All the outputs will be provided overall and by treatment phase (induction, consolidation and continuation).

The following summaries will be produced for hematology and biochemistry laboratory data (by laboratory parameter and treatment):

- For laboratory tests where grades are defined by CTCAE version 5.0, shift tables using CTC grades to compare baseline to the worst on-treatment value
- For laboratory tests where grades are not defined by CTCAE version 5.0, shift tables using the low/normal/high/(low and high) classification to compare baseline to the worst on-treatment value.

The following listings will be produced for the laboratory data:

- Listings of all laboratory data, with CTC grades and classification relative to the laboratory normal range. Lab data collected during the post-treatment period will be flagged.
- Listing of all CTC grade 3 or 4 laboratory toxicities

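### The by-phase laboratory shift tables measure from a pre-induction baseline, so in patients already cytopenic at diagnosis a new cytopenia in a later phase, chiefly single-agent continuation, can appear as no change or improvement.

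*SAP*

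**What the plan says.** SAP 2.1.1 (Baseline) fixes a single reference value for safety data: "For safety evaluations, the last non-missing assessment, including unscheduled assessments on or before the date of start of study treatment". The same section dates the start of study treatment to the "first date when a nonzero dose of any component of study treatment was administered". Under Protocol 4.1.2.2 that component is chemotherapy: "All screened patients will start induction therapy with chemotherapy (daunorubicin and cytarabine) from Day 1 to Day 7". The safety baseline is therefore at or before Day 1 of induction, not Day 8, when midostaurin or placebo begins.

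SAP 2.8.3 (Data analysis) calls for "shift tables using CTC grades to compare baseline to the worst on-treatment value", with a low/normal/high version for ungraded tests. It splits the laboratory results as follows: "All the outputs will be provided overall and by treatment phase (induction, consolidation and continuation". Protocol 10.5.3.3 has the same baseline-to-worst contrast but does not mention a split by phase. Neither document defines a baseline for an individual phase.

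Entry to the later phases depends on blood counts. SAP 1.1.2.2 says of consolidation: "Each consolidation cycle will begin within two weeks following hematopoietic recovery". Continuation also waits for recovery, "following the final cycle of consolidation but no sooner than 14 days after the last dose of midostaurin/placebo" in the last consolidation cycle. In both cases recovery means ANC of at least 1.0 and platelets of at least 100 x 10^9/L.

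**The concern.** A shift table shows how many patients got worse. It does so only if its starting value describes the patient at the start of the period tabulated. Here the starting value for every phase is a count taken with untreated leukemia, when the disease itself may have lowered it. Before the patient enters consolidation or continuation, ANC and platelets must have recovered. If they then fall, the table compares the fall with the diagnosis value and can place the patient on the no-change diagonal or on its improvement side.

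This matters most in continuation. Safety during single-agent continuation is part of a stated secondary objective (Protocol Table 3-1), and it is the only phase in which Protocol Table 6-2 changes midostaurin/placebo dosing for hematologic toxicity.

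**Working it through.** The plan states no figure on this point, so there is nothing to reproduce. The check follows the dates and then the logic of the table.

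**1. Age of the baseline at continuation.** Count induction Day 1 as day 0. Assume one induction cycle, the minimum four weeks between cycle starts, and study drug taken through Day 21 of the last consolidation cycle.

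- Consolidation cycles start no earlier than days 28, 56 and 84, and day 112 for a fourth cycle.
- The last study-drug dose falls on cycle Day 21 (offset 20). Adding the 14-day gap gives 20 + 14 = 34.
- Three cycles (JALSG): 84 + 34 = 118 days. Four cycles (RATIFY): 112 + 34 = 146 days.

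On these assumptions the baseline is at least 118 or 146 days old when continuation begins.

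**2. How a new cytopenia is classified.** Let b be the pre-induction grade, e the grade at phase entry and w the worst grade in the phase. A new cytopenia means w > e. The table sees only b and w:

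| Worst grade in phase (w) | Shown as worsening if b is | No change if b is | Improvement if b is |
|---|---|---|---|
| 1 | 0 | 1 | 2 to 4 |
| 2 | 0 to 1 | 2 | 3 to 4 |
| 3 | 0 to 2 | 3 | 4 |
| 4 | 0 to 3 | 4 | never |

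A new cytopenia is not shown as worsening only when b is at least w. Grade 5 is not used for laboratory values (SAP 2.8.3), so a new grade 4 cannot appear as improvement. With the phase-entry grade e as baseline, every case with w > e is shown as worsening by definition.

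**3. Share affected.** If b is independent of w, the share of new grade 3 events not shown as worsening is P(b = 3) + P(b = 4), and the share of new grade 4 events is P(b = 4). The documents give neither probability. Three assumed distributions show only how much depends on them:

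| Assumed P(b=3), P(b=4) | New grade 3 not shown as worsening | of which shown as improvement | New grade 4 shown as no change |
|---|---|---|---|
| 0.10, 0.05 | 0.10 + 0.05 = 15% | 5% | 5% |
| 0.20, 0.20 | 0.20 + 0.20 = 40% | 20% | 20% |
| 0.30, 0.40 | 0.30 + 0.40 = 70% | 40% | 40% |

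These are illustrations, not estimates for this trial.

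**4. What else shows the event.**

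| Output | Depends on the pre-induction baseline? | Covers continuation? |
|---|---|---|
| Worst-grade totals of the by-phase shift table (SAP 2.8.3) | No | Yes |
| AE tables by phase, events newly recorded in the phase (SAP 2.8.1) | No | Yes |
| Listing of grade 3 and 4 laboratory values (SAP 2.8.3) | No | Yes, but not a summary |
| Cytopenia tables by cycle: platelets below 20, ANC below 0.5 x 10^9/L (SAP 2.1.1, 2.8.3) | No | No: induction and consolidation only |

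Continuation is the one phase without the threshold-based tables.

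**The case against.** The strongest reply is that the event count is already there. ANC and platelets must have recovered at entry, so a patient with a worst grade of 3 or 4 in a later phase fell during that phase. The table's column total gives that number by arm, and only the row is affected by the old baseline. This stands. What is lost is the classification of change, which is what a shift table adds to a simple count.

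The AE route also covers more than it first appears to. Protocol Table 6-2 requires midostaurin/placebo to be held for grade 4 neutropenia in continuation, and Protocol 8.1.2.1 makes a laboratory abnormality with a protocol-required hold a reportable AE. That event will therefore appear in the by-phase AE tables. Other falls in counts become AEs only if they meet the conditions in Protocol 8.1.1, such as clinical significance or need for therapy. The AE tables are thus a good but incomplete substitute.

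A third reply is that a phase-entry baseline is post-randomization and may already reflect earlier midostaurin or placebo cycles. An abnormality carried over would become the reference and show as no shift. This stands too. It is a reason to add a table rather than replace one, and to limit it to hematology, where low counts from active leukemia are the reason for the change.

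A reader might infer two stronger things. One is that new cytopenias in later phases are generally hidden; the classification above shows that this needs a baseline grade at or above the worst grade. The other is that an excess on midostaurin is shrunk. The documents do not support that: the same rule applies to both arms, no baseline grades or continuation event rates are given, and Protocol 1.2.1.2 reports that midostaurin did not increase the incidence or severity of cytopenias in the earlier phase III trial.

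**Conclusion.** The point holds in a limited form. The by-phase shift tables use a baseline that does not describe patients as they enter consolidation or continuation. For those already cytopenic at diagnosis, a new cytopenia can be tabulated as no change or, for worst grades below 4, as improvement. Patients with a baseline grade below the worst grade are still shown as worsening.

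The practical gap is mainly the hematology shift in single-agent continuation. Consolidation is better covered by the threshold-based tables. The conclusion rests on the SAP definitions, the recovery conditions and the absence of any phase baseline in either document. The size cannot be stated without the distribution of baseline grades, and no distortion of the comparison between arms has been shown. This is a worthwhile correction to a descriptive safety table. It does not affect the efficacy analyses.

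**What to change.** In SAP 2.8.3, keep all planned shift tables with the pre-induction baseline. Add, for hematology parameters in continuation and optionally in consolidation, a shift table from the last non-missing value before the first dose of study treatment in that phase to the worst value in the phase. Define this phase-entry value in SAP 2.1.1 beside the existing safety baseline, and footnote every shift table with the baseline it uses.

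No new data are needed for continuation, because Protocol Table 7-1 B already schedules hematology before its first cycle. The cost is one derived flag and an extra table, or two if consolidation is included. The downside is small: the phase-entry value is measured after randomization and may carry effects of earlier cycles, so the new table should be read beside the pre-induction one.

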## **On-treatment assessment/event and observation periods**

For all safety analyses, the overall observation period will be divided into three mutually exclusive segments:

1. **pre-treatment period:** from day of patient’s informed consent to the day before first dose of study treatment

2. **on-treatment period:** from day of first dose of study treatment to 30 days after last dose of study treatment
3. **post-treatment period:** starting at day 31 after last dose of study treatment.

Safety summaries (tables, figures) include only data from the on-treatment period with the exception of baseline data which will also be summarized where appropriate (e.g., change from baseline summaries). In addition, a separate summary for death including on treatment and post treatment deaths will be provided. In particular, summary tables for adverse events (AEs) will summarize only on-treatment events, with a start date during the on-treatment period (**treatment-emergent** AEs).

However, all safety data (including those from the post-treatment period) will be listed and those collected during the pre-treatment and post-treatment period will be flagged.

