10.5.3 Safety objectives

10.5.3.1 Analysis set and grouping for the analyses

For all safety analyses, the safety set will be used. All listings and tables will be presented by treatment arm.

The overall observation period will be divided into three mutually exclusive segments:

- pre-treatment period: from day of patient's informed consent to the day before first dose of study treatment
- on-treatment period: from day of first dose of study treatment to 30 days after last dose of study treatment
- post-treatment period: starting on day 31 after last dose of study treatment.

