**Figure 1-1 Independent Safety Committee review in Part 1 safety evaluation part (Japan only)**

### 1.1.2 Part 2: Randomized Part

For the part 2 of the study, the start of patient enrollment in countries outside Japan will be concurrent with the start of the part 1 in Japan. The part 2 in Japan will begin only after the Independent Safety Committee agrees that midostaurin in combination with chemotherapy is adequately tolerated in Japanese patients. Novartis will report the decision to the full Study Steering Committee ([\[study protocol Section 8.7\]](#)).

Patients meeting all eligibility criteria (except FLT3 mutation) may begin the study treatment with chemotherapy. The FLT3 mutation status will be evaluated in a Novartis designated laboratory.

Patients who are determined to have AML with a FLT3 mutation (ITD and/or TKD) will be randomized on Cycle 1 Day 8 (first cycle of induction therapy) and will be assigned to midostaurin or placebo by using a stratified randomization according to FLT3 mutation and treatment regimen (see [\[study protocol Section 2.2\]](#)).

- Patients who are determined to have AML without a FLT3 mutation or with an unknown FLT3 mutation status by Cycle 1 Day 8 will be discontinued from the treatment.

Outside Japan, only the RATIFY regimen will be used.

During Part 1 (implemented in Japan only), safety and tolerability of midostaurin with the JALSG or with the RATIFY regimen will be assessed. There is no requirement for a minimum number of patients treated with each regimen. It is therefore possible, for example, that Part 1 will be completed only with patients treated with JALSG or only with patients treated with

[figure not shown]
RATIFY. If the ISC endorses proceeding to Part 2, then investigators in Japan may choose either RATIFY or JALSG for future patients. Once patients are enrolled in the study, their regimen must not be switched during the course of the study.

The study will include:

- Screening phase (7 days);
- Treatment phase composed of up to 18 cycles of midostaurin/placebo treatment in combination with chemotherapy (daunorubicin and cytarabine) during induction and consolidation and alone during continuation and 30 days safety follow up from last dose of study treatment (daunorubicin or cytarabine or midostaurin/placebo);
- Follow up phase for continued remission and survival.

Refer to [Figure 1-2](#) for study design.

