### **1.1.2.2 Treatment phase**

#### **Induction therapy**

All screened patients will start induction therapy with chemotherapy (daunorubicin and cytarabine) from Day 1 to Day 7, while the FLT3 mutation is being determined.

An Interactive Response Technology (IRT) system will be used to randomize patients to the study treatment groups and the patient eligibility checklist will be embedded into the IRT randomization process.

Only randomized patients (with FLT3 mutation) will receive midostaurin/placebo, orally twice a day, on days 8 to 21.

Patients who achieve CR already with induction cycle 1 will go directly to consolidation therapy without a second cycle of induction therapy. Patients who do not achieve CR with one cycle of induction will receive a second induction cycle with same treatment than in cycle 1.

Patients not achieving CR after induction 2 will discontinue study treatment and will be followed in safety follow-up and survival follow-up.

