**Table 1-1 Objectives and related endpoints**

Objective	Endpoint	Analysis
Primary		
Safety Evaluation part (Part 1, Japan only)		
To Evaluate the safety and tolerability of midostaurin in combination with daunorubicin/cytarabine induction and high-dose cytarabine consolidation in Japanese patients with newly diagnosed AML.	Incidence and severity of Safety Events, defined as death or serious adverse event leading to treatment discontinuation that occurs on or before Day 21 of the first Consolidation cycle and that is determined by the Independent Safety Committee to be definitely or probably related to midostaurin.	
Double-blind, randomized, placebo-controlled (Part 2)		
To Evaluate the efficacy based on event-free survival (EFS) of midostaurin versus placebo in combination with daunorubicin/cytarabine induction, with high-dose cytarabine consolidation, and with midostaurin single agent continuation therapy in newly diagnosed patients with FLT3-mutated AML.	Event-free survival (EFS) defined as the time from the date of randomization until an EFS event is observed. An EFS event is defined as a failure to obtain a CR within induction 2, relapse after CR, or death due to any cause, whichever occurs first.	Section 2.5
Secondary		

Objective	Endpoint	Analysis
Randomized part (Part 2)		
Determine overall survival (OS) in the two treatment groups	Overall survival (OS), defined as the time from the date of randomization to date of death due to any cause.	Section 2.7
Determine rate of complete remission (CR) in the two treatment groups	CR rate, defined as the proportion of patients with a CR according to Cheson criteria, at various timepoints.	
Determine cumulative incidence of relapse (CIR) in the two treatment groups	CIR (only for patients who have achieved CR after study treatment initiation), as measured from the date of first CR to relapse or death due to AML, whichever occurs first.	
Evaluate safety of midostaurin compared to placebo in combination with chemotherapy and as single agent continuation therapy	Frequency/severity of AEs, ECG and laboratory abnormalities.	Section 2.8
Evaluate the pharmacokinetics of midostaurin and its two major metabolites CGP52421 and CGP62221	Pharmacokinetic parameters for midostaurin and two major metabolites CGP52421 and CGP62221.	Section 2.10

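### Overall and induction AE tables by arm count the seven chemotherapy-only days before randomization, which weakens any-grade contrasts for terms common in that week; no supplementary table starts at the first midostaurin/placebo dose

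*SAP*

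**What the plan says.** SAP 2.1.1 restricts safety summaries to an on-treatment period "from day of first dose of study treatment to 30 days after last dose of study treatment". Protocol 10.5.3.1 sets the same period: "on-treatment period: from day of first dose of study treatment to 30 days after last dose of study treatment".

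In SAP 2.1.1, study treatment "will refer to treatment with daunorubicin, cytarabine, or midostaurin/placebo", and its start is "derived as the first date when a nonzero dose of any component of study treatment was administered". For every patient that is chemotherapy on induction Day 1.

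SAP 1.1.2 places randomization on Cycle 1 Day 8. SAP 1.1.2.2 adds: "Only randomized patients (with FLT3 mutation) will receive midostaurin/placebo, orally twice a day, on days 8 to 21". The Safety Set (SAP 2.2) requires randomization and at least one dose of study drug, so everyone tabulated by arm has first passed through a week of chemotherapy alone.

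SAP 2.8.1 counts a patient once per AE category. Its by-phase tables count AEs newly recorded between the start and end of the phase, and Protocol 6.1.5 starts an induction cycle at the start of study treatment. The AESI summaries (SAP 2.8.1.1) use the same on-treatment period. No by-arm AE table, overall or for induction, starts at the first midostaurin/placebo dose.

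**The concern.** An event that starts before the first study-drug dose cannot be caused by it. Because a patient counts once per term, an event in Days 1-7 already fills that patient's any-grade cell, and a later event of the same term adds nothing. The same expected number of such patients sits in both arms, so for terms common in that week a real excess on midostaurin looks smaller.

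Protocol 2.8 supplies a plausible example. Nausea, vomiting and diarrhea are named as midostaurin's main non-hematologic effects, and such events are reported in more than 50% of patients on intensive chemotherapy. With about 31 patients per arm, small differences in counts are what a reader of the safety tables has to interpret.

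**Working it through.** The plan states no figure on this point: no AE rates by day and no power for safety. The size is therefore shown over a range of assumptions.

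**Inputs**
- 62 patients randomized (SAP 2.1). An equal split is assumed, so 31 per arm.
- q = share of patients with the term in Days 1-7. This is not in the documents. It is taken as 2% to 30%, the same in both arms because it precedes randomization.
- Incidence from Day 8: assumed 20% on placebo and 35% on midostaurin.

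**General relation**

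RD (Day 1 table) = RD (any event from Day 8) − q × RD among patients who already had the event.

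**Case A: early and later events independent**

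The Day 1 table shows 1 − (1 − q)(1 − p) per arm, so the risk difference is multiplied by (1 − q). The SE is √[(a(1 − a) + b(1 − b))/31], where a and b are the tabulated incidences. The loss in patients is 31 × 0.15 × q, out of 31 × 0.15 = 4.65.

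| q | Placebo | Midostaurin | Difference (points) | Ratio | SE (points) | Loss (patients) |
|---|---|---|---|---|---|---|
| 0 (Day 8 table) | 20.0% | 35.0% | 15.0 | 1.75 | 11.2 | 0 |
| 2% | 21.6% | 36.3% | 14.7 | 1.68 | 11.4 | 0.1 |
| 5% | 24.0% | 38.3% | 14.3 | 1.59 | 11.6 | 0.2 |
| 10% | 28.0% | 41.5% | 13.5 | 1.48 | 12.0 | 0.5 |
| 20% | 36.0% | 48.0% | 12.0 | 1.33 | 12.4 | 0.9 |
| 30% | 44.0% | 54.5% | 10.5 | 1.24 | 12.6 | 1.4 |

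The SE rises by at most 1.5 points, so the main effect is attenuation and not added noise.

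**Case B: early events persist and cannot start again (q = 20%)**
- Day 1 table: 36% vs 48%, difference 12 points, ratio 1.33.
- Table of new events from Day 8 over all patients: 0.8 × 20% = 16% vs 0.8 × 35% = 28%, difference 12 points, ratio 1.75.
- The same table among patients at risk: 16/80 = 20% vs 28/80 = 35%, difference 15 points.

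Moving the window changes nothing here on the absolute scale over all patients. Only the ratio, or an at-risk denominator, recovers the contrast.

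**Correlated events**

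This check assumed 30% vs 50% from Day 8 and a Gaussian copula with correlation 0.6. At q = 30% the Day 1 table shows a difference of 13.5 points and a ratio of 1.32, against 14.0 points and 1.27 under independence. The result is similar.

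**Plausibility of q for gastrointestinal terms**

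Against a 50% chemotherapy background, q of 10% to 30% would mean that 0.10/0.50 = 20% to 0.30/0.50 = 60% of those events start in Days 1-7. Protocol 2.8 gives no timing, so that share is an assumption.

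**The case against.** The strongest defence is that the window fits the question asked. The objective reads: "Evaluate safety of midostaurin compared to placebo in combination with chemotherapy and as single agent continuation therapy". A window that covers the whole regimen is a legitimate way to describe that, and protocol and SAP agree on it. This stands. A reader might infer a contradiction, or a bias towards one arm, but the documents support neither: the wording matches, and pre-randomization events are balanced in expectation.

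A reader might also infer that no planned table isolates the study-drug period. That goes too far. By-phase tables count only newly recorded AEs, so consolidation and continuation already exclude Days 1-7, and continuation is study drug alone. The gap is confined to the overall and induction tables.

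Nor can it be said that risk differences shrink in every case; Case B shows when they do not. Nor is the time origin of the conditional AESI time-to-event analysis left open: the SAP's reference date for non-efficacy assessments and its censoring rule in 2.8.1.1 both point to the start of study treatment.

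On size, every rate is assumed. The loss of 0.1 to 1.4 patients compares with an SE of 31 × 0.1118 = 3.5 patients, and no formal safety test is planned. That is why the point is optional.

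Other planned outputs do not close the gap. "The study day will be displayed in the data listings", which identifies early events patient by patient but leaves the tables unchanged. The related-AE tables refer to study treatment, chemotherapy included. The exposure-response models in SAP 2.10 relate events to concentration and do not compare arms.

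**Conclusion.** The point holds as a sensitivity weakness in the overall and induction by-arm AE tables. For terms common in Days 1-7 the any-grade ratio is attenuated. The risk difference is attenuated too when study drug acts on patients who already had the event, by the factor 1 − q under independence. In the illustration, 15 points fall to between 14.7 and 10.5 as q goes from 2% to 30%. This rests on assumed rates, an equal split of 62 patients and equal early incidence in both arms.

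The effect is negligible for terms rare in Days 1-7. For near-universal terms such as cytopenias, any-grade counts have little room to differ in either window. Maximum-grade columns are less affected because worsening is recorded again (Protocol 8.1.1), but they are not protected if the highest grade is already reached before Day 8. The primary endpoint is untouched. The improvement is worthwhile but optional.

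**What to change.** Keep the pre-specified tables. Add Part 2 by-arm AE, SAE and AESI tables, labelled supplementary, overall and for induction, of events that newly start or worsen in grade on or after the first midostaurin/placebo dose. They need three rules:

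- **Improvement records.** Protocol 8.1.1 requires a new entry, with its own start date, when a grade 3 or 4 event improves. Entries that only document improvement must not count as new events.
- **Patients at risk.** For each term, show how many patients already had it ongoing at the first study-drug dose, and give percentages among those at risk. That status is fixed before any study-drug exposure.
- **Partial dates.** SAP Table 5-1 sets many partial AE start dates to the study treatment start, which can move a later event to Day 1. In these tables only, impute against the first study-drug dose.

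Two additions are optional: a version of the conditional AESI time-to-event analysis starting at the first study-drug dose, and ECG changes measured from the Day 8 pre-dose reading. Scheduled induction ECGs begin on Day 8 (Protocol Table 7-4), so the ECG gain is small.

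The cost is extra programming on dates already collected and one more set of tables. They would be added after unblinding at the primary analysis, so they can only be supplementary.
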